2.1 Quantitative Research Aims

Phase 1

Aim 1: Understand and finalize thresholds and criteria for alert system at the levels of Vital Patch, physIQ's pinpointIQ, monitoring RNs for CHF patients

Aim 2: Finalize process maps and workflows for nurse navigators and clinical care teams that optimize identifying high risk patients while minimizing provider burden

Phase 2

Aim 1: Determine if wearable technology deployed for 30 days in a high-risk patient population can augment 30-day readmission risk prediction and improve care processes via an escalating feedback protocol.

Aim 2: Calculate the return on investment of the remote monitoring solution

Aim 3: Perform a deep analysis of the full process to understand effectiveness, feasibility, efficiency and bottlenecks

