2.2 Experimental Plan and Methods

The goal of the study is to reduce readmission rates for high risk medical and surgical patients. Phase 1 will involve 5 high risk CHF patients. The goal of phase 1 is to understand how physIQ's platform Pinpoint IQ with a cascading set of alerts including the wearable device alerts, patient reported metrics, CAPE navigator or monitoring nurse alerts can be developed and improved upon to reduce the incidence of 30 day readmission. Phase 2 is the configuration and testing period before phase 3.

Phase 1

Phase 1 will assess the thresholds, process, and workflows of this cascading alert system. We will be enrolling 5 patients for this study at NorthShore University Health System.

CHF patients will be identified by an Enterprise Data Warehouse query that will report patients who meet specific inclusion and exclusion criteria daily. These criteria include being in the top 20% of the CAPE 30-day readmission risk prediction model, on the CHF service list at Evanston hospital, a patient of HF team, speaks English and does not have an implantable cardiomems device. The EDW query will be created and maintained by the clinical analytics team. These queries will be forwarded to the study coordinator who, when a qualifying patient is identified, will discuss with the CHF attendings regarding whether the patient is appropriate for this study. Patients will be approached by the study coordinator who will perform informed consent. If the patient is agreeable the patient will receive a kit from physIQ

prior to discharge. A Vital patch will be placed on the patient prior to discharge and the patch will be connected via blue tooth to the physIQ mobile device and pinpointIQ application. The study coordinator will teach the patient how to apply and remove the patch and what to do if there are issues with the patch. The study coordinator will also teach the patient how to use the mobile device and the physIQ application. The application will ask for the dry/current weight of the patient and this will be filled in prior to discharge.

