After discharge, CHF patients will be asked two questions every morning from the pinpoint IQ application. The pinpoint IQ platform will query patients about their current weight and if they actively have symptoms. These symptoms include chest pain, shortness of breath at rest, lightheadedness, dizziness, passing out, lower extremity swelling, orthopnea and postural nocturnal dyspnea. The monitoring nurse will evaluate the pinpoint IQ in the morning after the patient has filled out the questionnaire. They will evaluate the responses to the questions and the physiologic alerting system built by physIQ. There will be an algorithm built within physIQ's system that provides an alert to the monitoring nurse if the criteria from Table 1 are met.

Patients 1-5:
Any positive symptom
Example Question: Do you have any of the following symptoms? (multi-choice)
a. Chest pain b. Shortness of breath at rest c. Lower extremity edema d. Orthopnea (not able to lay flat) e. PND (Waking up in the middle of the night short of breath) f. Syncope (Passing out) g. Fatigue h. Vomiting i. Diarrhea
5 lb weight gain over dry weight (
Example Question:
What is your dry weight? What is your weight today?
A high risk alert
A predefined number of standard alerts in a day + 1-4 lb weight gain over dry weight

Table 1: Phase 1, physIQ alerts system for monitoring nurse for CHF

The actual thresholds for the high-risk alerts and the number of standard alerts may be changed from patient to patient based on how each case progresses and the density and frequency of alerts. Determining the optimal thresholds for these two types of alerts will be a key aim of phase 2. The goal is to maximize signal while minimizing noise.

If any of these conditions listed in Table 1 are met, the monitoring nurse will call the patient and go through a predefined note with the following data elements and questions.

monitoring nurse Alert System – CHF, phase 1

Do you currently have the following symptoms? (y/n)

- **Chest pain**
- **Shortness of breath at rest**
- Lower extremity edema
- Orthopnea (not able to lay flat)
- PND (Waking up in the middle of the night short of breath)
- **Syncope (Passing out)**
- Fatigue
- Vomiting
- Diarrhea

(Any Red Bolded symptoms results in phone call to clinical team and may physically see patients at home)

What is your dry weight? (Can look up patient's discharge weight and fill in or automate with data element)

What is your weight today? (Free text)

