In addition, the monitoring nurse will double the diuretic dosing if a patient has new symptoms of shortness of breath at rest, orthopnea, postural nocturnal dyspnea, or lower extremity swelling. The double diuretic dosing will also occur if weight gain increases by ≥ 5 lbs over dry weight. If the symptom question is met, then the patient will get a 3rd question on Day n+1 that asks if the symptoms are getting better, worse or the same. If the symptoms are getting worse, the monitoring nurse will escalate to the clinical care team with a phone call. If the symptoms are getting better or are the same, the double dose of diuretic will remain unchanged. If symptoms or weight gain normalize, the double dose of diuretic will be deescalated to the standard dosing regimen.

If there is a high-risk alert, then the monitoring nurse receives an alert, which will result in a phone call to the patients and note template with patients. The monitoring nurse alert will also occur if there are a certain number of alerts (to be determined and varied during patients 1-5) and 1-4 lbs of weight gain (to be determined and varied during patients 1-5). In addition, if patients have some combination of weight gain and standard alerts or a high-risk alert, then the doubling of diuretics will also occur. If patients have a combination of 1-4 lb weight gain and a set number of device alerts, we will stop diuretic dosing if weight gain normalizes back to dry weight. The process map for patients 1-5 is shown in Figure 1. Escalating and deescalating diuretic dosing will also be built into the same note template in addition to prompts for education to ensure a standardized process from the monitoring nurses. We also have a multiple-choice option for monitoring nurse to document the care plan for participants.

[figure not shown]

Figure 1: Process map for CHF Patient 1-5

If care is escalated to the clinical care team which includes Advanced Practice Nurses, Physician Assistants and Physicians, the care team will pursue various interventions including counseling, altering medication therapy, urgent visits to heart failure clinic ideally within 72 hours, and if no other available options readmission. These workflows will be left to the discretion of the clinical care team given the nuance in taking care of these high-risk patients and the existing relationship and prior history with

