Plan 
 3. Plan? Please select all that apply from the following options (multi-select) 
 a. Continue PO diuretic

- b. Increase PO diuretic
- c. Decrease PO diuretic
- d. Hold PO diuretic
- e. Start IV diuretic
- f. Was there a change or new addition of a BB
- g. Was there a change or new addition of a ACEI/ARB/ARNI
- h. Was there a change or new addition of mineralocorticoid receptor antagonists (MRAs)
- i. Start antibiotic
- j. Start breathing treatment

Other interventions (not medication related)

- a. Have monitoring nurse do in person visit
- b. Set up cardiology urgent visit
- c. Send patient to the ER
- d. Check labs
- e. Check imaging
- f. Other (free text)

Table 3. Mid-level CHF Note Template

For phase 1 and 2 there will be significant data collection that is part of this process to understand how our process maps result in outcomes. Learnings from these 20 patients will inform the final process for phase 3 CHF.

QUALITATIVE

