6.2 Data Transport via physIQ Android Mobile App and physIQ Platform

The physIQ Android mobile app is loaded onto an Android-based phone or tablet mobile device. The mobile device offloads vital sign data from the VitalPatch™ (via low energy Bluetooth) and uploads it using digital cellular or WiFi network to the cloud-based server. In addition to transmitting physiological data, the app also may present questionnaires to the patient that are answered directly within the app.

Upload via digital cellular network is secured with TLS cryptographic protocol between the mobile phones and the server. The physIQ platform is securely hosted in the Google cloud. The physIQ cloud stores the raw physiological telemetry data captured by the study device, and also stores analytical results generated by running that raw data through the physIQ Analytics Modules. All the telemetry and analytical results are stored separately from any personally identifiable information (PII) that an institution might choose to enter in the system. There is no requirement to enter PII in order to use the platform, as all data can be tracked solely by random ID as well. PHI will not be transmitted to physIQ for this process and the only data that will be transmitted is a random ID generated at NorthShore. NorthShore will maintain the key to the identifier. The data can only be obtained or viewed via secure authenticated login.

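### Alert thresholds are varied between patients in response to each case, so differences in alert burden between settings are confounded with differences between patients

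*Protocol*

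**What the plan says.** Section 2.2 (Phase 1, text after Table 1) states of the high-risk threshold and the standard-alert count that they "may be changed from patient to patient based on how each case progresses and the density and frequency of alerts". Further on, the same section has the nurse alerted when "there are a certain number of alerts (to be determined and varied during patients 1-5", combined with a small weight gain that is also to be varied over those patients. The first statement is a permission and the second an intention. The only selection criterion is qualitative: more signal, less noise.

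The protocol disagrees with itself on where thresholds are settled:

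- Section 2.1 makes it a phase 1 aim to "Understand and finalize thresholds and criteria for alert system", and section 2.2 says "Phase 1 will involve 5 high risk CHF patients".
- Section 2.2 also says "Determining the optimal thresholds for these two types of alerts will be a key aim of phase 2".
- Section 2.2 closes its account of phases 1 and 2 with "Learnings from these 20 patients will inform the final process for phase 3 CHF". Section 4.3.1 gives 20 as the total enrolment.

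On data, section 6.2 says "The physIQ cloud stores the raw physiological telemetry data captured by the study device", together with the analytical results. Section 5.2 returns physiologic, alert and patient-reported data to the site. Sections 4.7 and 5.1 have all data destroyed after the study. Under section 2.2, a high-risk alert, or standard alerts with weight gain, can lead to a change of diuretic dose.

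**The concern.** If the setting changes when the patient changes, setting and patient are the same contrast. A quieter next patient then looks like a better threshold, and a busier one like a worse threshold. The change is also triggered by what was just seen, so it is not independent of outcome: a change made after an unusually noisy case will tend to be followed by a calmer one whatever the setting.

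At stake is a main product of the early phases, the thresholds carried into phase 3. The smaller the number of patients behind them, the more they reflect who happened to be enrolled.

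**Working it through.** The protocol gives no precision target or derivation for the thresholds or for the five patients, so there is no figure to reproduce. The checks below show the size of the problem. Inputs from the protocol are 5 patients in phase 1 (section 2.2), 20 in all (4.3.1), 30 days of post-discharge data (4.3.1) and readmission of 15–30% (1.2, taken here as a 30-day rate). Alert rates and between-patient variation are not given and are **assumptions**.

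**1. Alert burden, one patient per setting.** Assume 2 alerts per day at the looser setting and a stricter setting that truly fires 70% as often. Expected counts over 30 days are 2 × 30 = 60 and 0.7 × 60 = 42. With a lognormal patient effect of coefficient of variation CV, s² = ln(1 + CV²), and

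SE(log ratio) = √(2s² + 1/60 + 1/42); approximate 95% range = 0.70 × exp(±1.96 SE).

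A simulation of 200,000 runs gave the last three columns. Wrong order means that the stricter setting appears to fire at least as often as the looser one.

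| CV | s² | SE | Range by formula | Range simulated | Wrong order, 1 v 1 patient | Wrong order, 3 v 2 patients |
|---|---|---|---|---|---|---|
| 0.25 | 0.061 | 0.40 | 0.32–1.54 | 0.31–1.55 | 19% | 8% |
| 0.50 | 0.223 | 0.70 | 0.18–2.75 | 0.17–2.83 | 31% | 21% |
| 1.00 | 0.693 | 1.19 | 0.07–7.28 | 0.06–7.88 | 39% | 31% |

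The 3 v 2 column splits all five patients between only two settings. Confounding lessens but remains.

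**2. Same question, both settings replayed on all five patients.** Wrong order 0%; 95% range of the ratio 0.65–0.75 (0.64–0.76 at CV 1.0). The 0% holds by construction, since alerts at the stricter setting are a subset of those at the looser one. The narrow range also assumes the same true ratio in every patient and all 5 × 30 = 150 patient-days usable. Variation in the ratio, or days set aside after treatment changes, would widen it.

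**3. Sparser alerts.** With 0.3 alerts per day (9 in 30 days) and a between-patient SD of the log rate of s = 0.3, 0.5 or 1.0, SE = √(2(s² + 1/9)) = 0.63, 0.85, 1.49. Two settings tried in one patient each must differ by exp(1.96 SE) = 3.5-, 5.3- or 18.6-fold to exceed chance at the 95% level.

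**4. Events, which replay does not add.**

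- Five patients: expected readmissions 5 × 0.15 = 0.75 to 5 × 0.30 = 1.5. The chance of none is 0.85⁵ = 44% to 0.70⁵ = 17%; the chance of at least two is 16% to 47%.
- Exact 95% lower limit for sensitivity when all k events are flagged is 0.025^(1/k): 2.5% for 1 of 1, 16% for 2 of 2.
- Twenty patients: 3 to 6 events expected; lower limit 29% for 3 of 3, 54% for 6 of 6.

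**The case against.** Four replies have force.

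- **Five patients is only one reading.** The sentence that follows the quoted rule moves the optimisation to phase 2, and section 2.2 later refers to 20 patients. A reader might infer from section 2.1 that thresholds will be fixed on five; the protocol does not settle this. The conflict itself stands.
- **One patient per setting is the extreme case.** Section 2.2 says that settings may change, so one setting could cover several patients. Nothing bars a later analysis of stored data, and an analysis plan that is not shown might contain one. Adaptive tuning in a pilot without an inferential claim is a legitimate choice. This limits the size of the problem; it does not separate setting from patient.
- **Missed deterioration is not invisible.** A reader might infer that tuning on alert load sees only false alarms and must drift towards quieter settings. The documents do not support that. Symptoms and weight are asked every morning, Table 1 triggers a nurse call on these alone, the Table 2 note records alert counts for the last 24 hours, and readmissions are collected (4.3.1). A symptomatic patient with no device alert is therefore captured as structured data, and tuning also looks at how the case progresses.
- **Replay is not a full cure.** Acted-on alerts change diuretic dosing, so later telemetry depends on the live setting. If an alert led to treatment and no event followed, a stricter replayed setting would drop that alert without recording a miss, and a useful alert would look like noise.

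The alert rates and CVs above have no source in the protocol. Analytics measured against each patient's own baseline (6.3) could reduce between-patient variation, which is why a range is shown.

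**Conclusion.** The concern holds for alert burden. Varying settings between patients in response to their course confounds setting with patient. Under the stated assumptions, a comparison of single patients ranks two settings wrongly in 19–39% of runs, and a split of five patients over two settings does so in 8–31%. The problem is worst if section 2.1 governs and shrinks if all 20 patients are used; the two sections must be reconciled.

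It would go too far to say that replay removes the problem at no cost. It removes the confounding for alert counts only. It cannot show nurse response or outcomes under settings that were not live, and it leaves sensitivity inestimable with 0.75–1.5 expected readmissions in five patients and 3–6 in twenty. No view is taken on which threshold or diuretic rule is right.

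**What to change.** 1. Reconcile sections 2.1 and 2.2 on the phase, and the number of patients, on which thresholds are finalised.
2. Leave live settings to the clinical team, but log each one with its start and stop dates for each patient.
3. Before the data are destroyed, replay a prespecified grid of high-risk cut-offs and standard-alert counts on the stored data of all enrolled patients. Report alerts per patient-day for every setting on the same patient-days.
4. Flag or censor data after the first alert-driven treatment change, and state how many patient-days remain.
5. Report readmissions and other events, and symptom or weight triggers, without a preceding device alert within a fixed look-back, as descriptive only. State that an alert followed by successful treatment is not to be counted as noise.

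**Cost.** No extra patients and no change to care. Analyst time is needed, as is an export or rerun of the vendor's index values: sections 5.1 and 5.2 list vital, alert and patient-reported data for transfer but do not say that the analytical results stored in the vendor cloud are included.

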Weight change over dry weight? (y/n or drop down)

- ≥ 5 lbs
- 1-4 lbs
- At or below dry weight

(Any Symptom + ≥ 5 lbs weight change over dry weight)

Diuretic Medication? (y/n)

- Are you on the same (standard) diuretic dose you were placed on at discharge or by your heart failure physician after an outpatient appointment?

(If on same medication and either new symptoms of shortness of breath at rest, lower extremity edema, orthopnea, PND or ≥ 5 lbs weight gain or 1-4 lbs weight gain with a prespecified number of standard alerts or a high risk alert than ask patient to double diuretic dose)

(If on double diuretic dose and no longer symptomatic AND back to dry weight, deescalate diuretic dose to discharge dose)

If you had symptoms yesterday are your symptoms better, worse, or the same today? (drop down for 4 choices: better, worse, same, N/A)

(If worse phone call to care team)

Med adherence? (y/n)

- Have you missed any diuretic doses in last 24h
- Have you missed any medication doses in last 24h

(Any symptom + not adherent to any meds) Reinforce importance of med adherence

Changes in diet, Salt intake? (y/n)

- Are you eating meals that you are making at home?

(Any symptoms + not eating meals that you are making at home) Reinforce importance of low salt diet and eating meals that you are making at home

Alerts over last 24 hours

- Was a high risk alert triggered (y/n)
- How many high risk alerts triggered: (Numerical answer)
- Were any standard alerts triggered (y/n)
- How many standard alerts triggered: (Numerical answer)

(High risk alert triggered)**Plan: (Multiple choice)**

- a. Phone call to clinical team for concerning symptoms
- b. Escalate or double diuretic dose
- c. Deescalate diuretic dose
- d. Reinforce med adherence
- e. Reinforce dietary adherence
- f. Other (free text)

Table 2: Phase 1, monitoring nurse nurse alerts system for clinical team for CHF

Table 2 will be configured into a note template within EPIC that allows for data elements to be captured. If any of the black or red bold logic is met the note will be forwarded to the clinical team with a high priority. If any of the red bolded elements are elicited from the patient, then the monitoring nurse will call the CHF clinical team for immediate communication. All notes will be forwarded to the clinical care team.

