these providers. There are some standardized workflows that will be followed by the care team that are of note. If the patient has diuretic dose escalated for 3 days, then the clinical care team will make sure patient has a basic metabolic panel ordered to make sure patient's renal function is stable on the higher diuretic dose. We created a standardized note template for mid-level providers as part of the escalation pathway (Table 3). Also, all messaging from the monitoring nurse will be forwarded to the heart failure clinical pool and/or CHF APP pool per protocol to create the most rapid response back to the patient if required.

Cardiovascular symptoms not related to CHF Is the patient having any concerning cardiovascular symptoms not related to CHF? (y/n)
Pulmonary symptoms Is the patient having any concerning pulmonary symptoms not related to CHF? (y/n)
Infectious symptoms Is the patient having any symptoms concerning for an infection (eg: fever, dysuria, productive cough, diarrhea, vomiting, rash, or flu-like symptoms)? (y/n)
Urine output Does the patient have decreased urine output or are they not responding to their diuretic dose? (y/n)
Hematologic symptoms (such as bleeding and thrombosis) Is the patient having any concerning hematologic symptoms? (y/n)
Medication adherence questions 
 • In the last week has the patient missed any diuretic doses (eg: lasix, bumex, spironolactone)? (y/n/na) • In the last week has the patient missed any beta blocker doses (eg: metoprolol, carvedilol)? (y/n/na) • In the last week has the patient missed any ACE/ARB doses (eg: enalapril, lisinopril, benazepril, captopril, quinapril, irbesartan, losartan, olmesartan, valsartan)? (y/n/na)
Self-Care 
 1. Did the patient ask any questions related to self-care? (y/n) 2. Did a family member or caregiver ask any questions related to self-care? (y/n) 3. Did the patient or a family member or caregiver know their medications? (y/n) 4. What led to your communication with the patient? (monitoring nurse recommendation, patient called, abnormal lab finding, other)
Assessment 
 1. What do you think is the cause of the patient's decompensation? (HF exacerbation, cardiovascular non-HF, pulmonary, infectious, renal, other) 2. On a scale of 1 to 5 how confident are you in this choice? 1 being least confident, 5 being extremely confident (select number 1-5 from drop down menu)

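### The nurse's diuretic-doubling line leaves open whether a high-risk alert also needs weight gain, and under either reading no visible line defers doubling for vomiting or diarrhea

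*Protocol*

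**What the plan says.** All the relevant text is in Protocol section 2.2.

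- **When the nurse calls (Table 1).** A high-risk alert is a row of its own. The small weight gain is paired with the other alert type: "A predefined number of standard alerts in a day + 1-4 lb weight gain over dry weight". Any positive symptom also prompts a call, and the list includes vomiting and diarrhea.
- **When the dose is doubled (Table 2).** For a patient on the usual diuretic dose, the triggers are a new congestive symptom (breathlessness at rest, leg edema, orthopnea or PND), a gain of 5 lb or more, or "1-4 lbs weight gain with a prespecified number of standard alerts or a high risk alert than ask patient to double diuretic dose". The text after the table restates the last part: "if patients have some combination of weight gain and standard alerts or a high-risk alert, then the doubling of diuretics will also occur".
- **When the dose comes down.** Table 2 says: "If on double diuretic dose and no longer symptomatic AND back to dry weight, deescalate diuretic dose to discharge dose". The text after it links normalized symptoms and normalized weight with *or*. For the route of 1-4 lb gain plus device alerts, it gives a stop based on return to dry weight. For symptoms on the following day it says: "If the symptoms are getting better or are the same, the double dose of diuretic will remain unchanged".
- **What the clinical team sees.** All notes are forwarded, some at high priority. Worsening symptoms and the red-bolded symptoms prompt a phone call. A metabolic panel is tied to this condition: "If the patient has diuretic dose escalated for 3 days". The mid-level template (Table 3) asks "Is the patient having any symptoms concerning for an infection (eg: fever, dysuria, productive cough, diarrhea, vomiting, rash, or flu-like symptoms" and offers holding the oral diuretic as a plan option.

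**The concern.** This is a medication instruction that a nurse carries out by telephone. Two nurses could read it differently for the same patient: one doubles on a high-risk alert alone, the other waits for weight gain. Under the first reading, the dose can rise in a patient with neither weight gain nor a congestive symptom.

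The second gap does not depend on that choice. A patient losing fluid through vomiting or diarrhea can meet a doubling trigger. The nurse will have asked about both symptoms, yet the dosing line makes no use of the answer. The clinicians' own template treats the same symptoms as worth asking about and lists holding the diuretic as an option, but nothing visible makes the nurse wait for that judgment.

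The study is affected too. Phase 1 is meant to tune the alerts in 5 patients, and the note template is meant to standardize what the nurses do. Tuning high-risk alerts is hard to interpret if the action that follows such an alert is not fixed.

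**Working it through.** The protocol gives no figure to reproduce here. The check lists every combination of the rule's inputs and counts where each reading doubles the dose.

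**Inputs (Tables 1 and 2), patient on the standard dose:** new congestive symptom (yes/no), weight (5 lb or more, 1-4 lb, at or below dry), standard-alert count met (yes/no), high-risk alert (yes/no). States: 2 × 3 × 2 × 2 = 24.

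**Narrower reading (weight required):** symptom OR ≥5 lb OR [1-4 lb AND (standard alerts OR high-risk alert)].

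**Wider reading (alert alone counts):** symptom OR ≥5 lb OR [1-4 lb AND standard alerts] OR high-risk alert.

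| Congestive symptom | Weight | States | Narrower doubles | Wider doubles |
|---|---|---|---|---|
| yes | any | 12 | 12 | 12 |
| no | ≥5 lb | 4 | 4 | 4 |
| no | 1-4 lb | 4 | 3 | 3 |
| no | at or below dry | 4 | 0 | 2 |
| **Total** | | **24** | **19** | **21** |

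The 21 − 19 = 2 states that differ are both a high-risk alert, at or below dry weight, without a congestive symptom.

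**Adding vomiting or diarrhea (yes/no)** gives 24 × 2 = 48 states. Neither reading uses this input, so each count doubles: 2 × 19 = 38 and 2 × 21 = 42. Of the 42 − 38 = 4 differing states, 2 include vomiting or diarrhea. Within the 24 states where one is present, doubling follows in 19 (narrower) or 21 (wider).

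**Step-down under the wider reading.** Take a patient with no symptom at all, at or below dry weight, with a high-risk alert. The dose is doubled. At the next contact the patient is on the double dose, symptom-free and not above dry weight, so both the *and* rule in Table 2 and the *or* rule in the text bring the dose down. No visible stop depends on the alert clearing. The doubling and step-down lines never apply at the same moment, because one needs the standard dose and the other the double dose. The difficulty is one of sequence.

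**Which reading do the passages favor?**

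- For the wider: Table 1 lists the high-risk alert alone and ties the 1-4 lb gain to standard alerts only. But Table 1 sets calls, not doses.
- For the narrower: the restatement in "if patients have some combination of weight gain and standard alerts or a high-risk alert, then the doubling of diuretics will also occur" speaks of a combination with weight gain; "If on double diuretic dose and no longer symptomatic AND back to dry weight, deescalate diuretic dose to discharge dose" presumes a weight that had risen; and the stop for the alert route is based on weight.
- Not visible: "The process map for patients 1-5 is shown in Figure 1", but that figure is missing from the text at hand, as is the color coding of Table 2.

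The visible text does not settle it.

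**The case against.** The strongest reply is that the passages on dosing lean toward requiring weight gain, so the patient at dry weight would not be doubled at all. That carries weight, and it is why the alert-alone reading cannot be presented as what the protocol instructs. It does not remove the ambiguity, and it does not touch vomiting and diarrhea, where 19 of 24 states still double.

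Second, safeguards exist. Every one of those 24 states already prompts a nurse call, and the nurse's plan list includes calling the clinical team and a free-text option. Breathlessness at rest is among the bolded symptoms that lead to a call. Table 2 also has its own line for a triggered high-risk alert; depending on its lost color, that may already send a high-priority note or require an immediate call. All this lowers the risk. What remains is that no visible text puts the clinician's decision before the doubling.

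Third, Phase 1 exists to settle thresholds and workflows, and acting on an alert before weight moves may be the purpose of the device. Both points are fair. Open thresholds are not an error, and doubling on an alert alone is a choice the clinical team may make. But how the conditions combine is not a threshold, and a choice of this kind has to be written down.

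A reader might also infer that a vomiting patient stays on the double dose for as long as the vomiting lasts. The documents do not support that. It requires Table 2's *and* rule and a meaning of symptomatic that covers all nine listed symptoms. Under the *or* wording in the text, or if only the four congestive symptoms count, the dose can come down at dry weight.

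**Conclusion.** The concern holds in two parts. First, the doubling line has two readings, and they differ for patients with a high-risk alert, at or below dry weight and without a congestive symptom: 2 of 24 standard-dose states, or 4 of 48 once vomiting or diarrhea is an input. Second, under either reading no visible line defers doubling when the patient reports vomiting or diarrhea.

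Two stronger claims should not be drawn. The protocol does not clearly order doubling on an alert alone. Nor is the patient without protection: notes, calls and labs after 3 days of escalation are all provided for, though none is stated as a condition of doubling.

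The state counts show where the rule acts, not how often. The protocol gives no high-risk alert rate, so the number of the 5 Phase 1 patients affected cannot be estimated. The conclusion rests on the visible text; Figure 1 or the color coding could settle the grouping or show an earlier call. The written rule would still need to agree with them. Because this is a dosing instruction and the repair is small, it should be corrected.

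**What to change.** In Table 2 and in the text after it:

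1. **State the grouping.** Either require the 1-4 lb gain with both alert types, or, if an alert alone is meant to count, have the nurse call the clinical team, who decide the dose and when the increase stops.
2. **Cover vomiting and diarrhea for every trigger.** Whatever prompts the doubling (symptom, weight or alert), if the patient reports either one, the nurse calls the clinical team before asking for a double dose.
3. **Make the sources agree.** Use one de-escalation rule in place of *and* in Table 2 and *or* in the text, and check that Figure 1 shows the same logic.

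The cost is a few reworded lines and a revised figure; the call to the clinical team is already in Table 2's plan list. The downside is a few more calls and possibly a short delay in treating early congestion that an alert detects before weight or symptoms change.
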